- To assume responsibility for the proper conduct of the study and not to deviate from the procedures described in the protocol.
- I am thoroughly familiar with the investigational product(s) as described in the protocol, Investigator's Brochure and any other relevant information sources provided to me.
- I am aware of and will conduct the study in compliance with the protocol, ICH GCP guidelines and all applicable regulatory requirements.
- I agree to permit monitoring and auditing of the study by the Sponsor and its designates, and inspection by appropriate regulatory authority (ies).
- I agree to ensure that all persons assisting with the conduct of the study are properly qualified for their function.

Investigator Name & Signature:

Principal Investigator: [name] Print/Type Name

Signed: _____

Signature

[figure not shown]
Date:

PROTOCOL SUMMARY

Title:	A Prospective, Multicenter, Randomized, Triple-Blinded, Placebo-
	Controlled study of IL-1RA Treatment in Patients with Acute ACL
	Tear and Painful Effusions
Précis: Objectives:	This study aims to establish efficacy and timing of administration, to reduce post-injury pain, decrease inflammatory biomarkers in ACL injured patients undergoing ACL reconstruction and correlate function, patient reported outcomes and MRI findings at 1 years after ACL injury. The study population will include 40 subjects, ages 14-40 who will be randomized into 2 groups (20 subjects per group). 1. Test the efficacy of a treatment protocol using IL-1ra and knee arthrocentesis to alleviate inflammation related knee pain and improve patient-reported outcomes (PRO) following ACL rupture. 2. Determine if intra-articular IL-1ra therapy improves levels of a panel of inflammatory, meniscus and cartilage metabolism, and oxidative stress biomarkers as measured in synovial fluid, serum and urine from patients immediately after ACL injury (baseline, 2 weeks
	after injury and at 1 and 2 years after surgery).3. Answer the question if MRI T1rho changes correlate with synovial biomarker levels and show predictive value for the overall subject patient outcome at 2 years.
Endpoint	Primary endpoint : Change in Patient reported outcomes as measured by KOOS- Symptoms
	Secondary endpoints: KOOS QOL, KOOS-pain, KOOS-Sports/Rec, Biomarker levels in synovial fluid, serum and urine at time of surgery MRI T1rho changes at 2 years
	Study Stopping Criteria

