4.2 STUDY ENDPOINTS

4.2.1 PRIMARY ENDPOINT

Patient reported outcomes as measured by KOOS-Symptoms

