7.3 STUDY SCHEDULE

7.3.1 SCREENING/ENROLLMENT

Visit 1 Screening 1-28 days following injury)

- Obtain informed consent and assent, if necessary, of potential subjects
- Review medical history to determine eligibility based on inclusion/exclusion criteria.
- Review medication history to determine eligibility based on inclusion/exclusion criteria.
- Perform medical examinations and collect vital signs as needed to determine eligibility based on inclusion/exclusion criteria. All subjects must have a clinical exam that is consistent with an ACL tear.
- Collection of urine and blood for laboratory testing. Women of child bearing potential will be given a urine pregnancy test. Test must be negative in order to enroll into the study.
- Subjects will have the following assessments: range of motion, knee instability (Lachman's test) and standardized MTP-2 weight bearing x-rays.
- Standard questionnaires including the KOOS, IKDC, VR-12 and a Likert pain scale.
- Research knee MRI

Following the review of above assessment results and a review of inclusion/eclusion criteria, subjects will be randomized into 1 of 3 treatment groups. Following randomizing, subjects will undergo a knee aspiration and will receive their first dose study medication.

Visit 2 (day of surgery or 4-6 weeks post injury)

- Knee aspiration (in the operating room under anesthesia)
- Patient reported outcomes (PROs) administered prior to surgery
- KOOS, IKDC, VR-12 and a Likert pain scale administered prior to surgery
- Biomarkers (urine and blood) pre-operatively
- Review for AE's and SAE's
- ROM will be performed prior to surgery

Visit 3 (4-14 days After Visit 2)

- Knee aspiration (if clinically indicated)
- Biomarkers (urine and blood)
- Review for AE's and SAE's
- ROM will be performed

Visit 4 (6 month After Visit 2+/- 2 weeks)

- Patient reported outcomes (PROs) administered
- KOOS, IKDC, VR-12 and a Likert pain scale administered
- Review for AE's and SAE's

• ROM will be performed

Visit 5 (12 monthsAfter Visit 2+/- 2 weeks)

- ÀRI
- Patient reported outcomes (PROs) administered
- KOOS, IKDC, VR-12 and a Likert pain scale administered
- Biomarkers (serum and urine only)
- Review for AE's and SAE's
- ROM will be performed

Visit 6 (24 month After Visit 2+/- 2 weeks)

- MRI
- Patient reported outcomes (PROs) administered
- KOOS, IKDC, VR-12 and a Likert pain scale administered
- Biomarkers (serum and urine only)
- Review for ÀE's and SAE's
- ROM will be performed

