10 STATISTICAL CONSIDERATIONS

10.1 STATISTICAL AND ANALYTICAL PLANS

10.1.1 GENERAL APPROACH

Sample Size and Power Analysis - The primary outcome aim of the study is to determine if treatment with the study medication results in greater improvements in patient-reported outcomes one year following surgery. We will use the validated Knee Osteoarthritis and injury Outcome Score (KOOS),[27] which is a self-administered, knee-specific instrument that evaluates the course of knee injury and treatment outcomes. To reduce the risk of an underpowered RCT, an a priori sample size estimation was calculated from data collected from recent studies of ACL-injured and -reconstructed patients.[28-32] The previously published oneyear KOOS Quality of Life Scores are 60.2 ± 24.2 [31] and the minimal detectable change of this instrument is 7.2 [32]. Assuming that the standard deviation of the change scores between the day of surgery and one year postoperative visits will be 20% of the standard deviation of the standard deviation of the one-year KOOS Quality of Life Scores ($.2 \times 24.2 = 4.8$), a sample size of 16 patients per group (32total) would be at least 80% powered to detect a difference of 7.2 points between the treatment group and the control group (One-way ANOVA model with alpha = 0.05, Effect size = 7.2/4.8 = 1.5, G*Power 3.0.10). This sample size would adequately power the study for the primary outcome variable, but would also adequately power the study for the second aim of the study. The second aim of the study is to compare chondrodegenerative biomarkers between groups at the 1 year follow up. We have previously observed large effect sizes between groups in preliminary studies (ES = 1.34), and a sample size of 32 patients (16 per group) would be at least 80% powered to detect effect sizes of this magnitude. However, to protect against an underpowered study due to patient attrition, we will monitor compliance and potentially enroll up to 20 patients per group in order to adjust for attrition. Patient costs will not occur until sample or MRI analysis.

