The power calculations include several caveats. First, for purposes of power calculation, we did not assume a full repeated measures analysis, but instead analyzed at a single time point (oneyear follow-up). Second, we note that in trials such as this, the power of a non-parametric analysis is never much lower than its parametric analog (the "asymptotic relative efficiency" of the Wilcoxon test is at least 0.95), leading us to conclude that our parametrically based power calculations should apply with equal force to a non-parametric analysis.

Statistical analyses - Results from a sample of this size may not be normally distributed. Therefore, non-parametric statistical measures may be used. Primary outcome measures evaluating for change in KOOS will be assessed at multiple points and will be analyzed for change between groups using Friedman two-way ANOVA for repeated measures. Synovial fluid analyses comparing the three groups at five time points will be analyzed using the Wilcoxon Signed Rank Sum Test with Hochberg corrections for multiple time points. Alternatively, if results are normally distributed or can be transformed (e.g., by log transformation) to meet the criteria for normality for parametric analysis, then repeated measures ANOVA will be utilized comparing treatment groups. P-values of less than or equal to 0.05 will be considered statistically significant.

Predicted Results: IL-1ra, while potent, has had mixed results in the treatment of established OA, possibly due to it's short half-life in vivo. In this trial, we expect that an early intervention with IL-1ra will effectively block the deleterious cascade of joint degradation events after joint injury. We expect a significant effect of IL-1ra on post-injury pain and concomitantly an increase in patient-reported outcomes due to the improved early function

Minimization of bias: Due to the randomized study design and the blinding of the investigator and patient to the drug used, we hope to eliminate any investigator or subject bias. Using broad and previously established enrollment criteria we hope to reduce selection bias to a minimum while protecting potentially vulnerable individuals through the exclusion criteria. Procedural bias and measurement bias will be reduced by the multicenter design and the blinded data analysis.

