10.1.2 ANALYSIS OF THE PRIMARY EFFICACY ENDPOINT(S)

A safety review of treatment Groups 1 and 2will be performed. Safety endpoints will be monitored at each study visit and at each monitoring visit.

Study Stopping Criteria

- local intolerance of the administered Kineret or any sign of allergic response.
- development of signs and symptoms before the second time point preventing the second administration of the study drug.
- Any patient reported SAE after the first or second administration of the study drug.
- Diagnosis with any condition as outlined in the exclusion criteria during the course of the initial 2 weeks of study enrollment.

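### The primary KOOS-Symptoms analysis names no baseline-adjusted comparison of the two arms, although a pre-injection score is collected at Visit 1

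*Combined protocol and SAP*

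**What the plan says.** The Protocol Summary gives the primary endpoint as "Change in Patient reported outcomes as measured by KOOS- Symptoms". Section 4.2.1 gives it as "Patient reported outcomes as measured by KOOS-Symptoms", without the word change. Neither names a time point or a reference visit.

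On analysis, section 10.1.1 states that "Primary outcome measures evaluating for change in KOOS will be assessed at multiple points and will be analyzed for change between groups", with Friedman's two-way ANOVA as the method. If the data are normal or can be transformed, "then repeated measures ANOVA will be utilized comparing treatment groups". Section 10.1.2, headed as the primary efficacy analysis, has no efficacy model. It opens with "A safety review of treatment Groups 1 and 2will be performed" and continues with stopping criteria. Section 10.1.3 is marked not applicable. Section 10.2.1 describes permuted blocks and names no stratification factor.

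On data, the Visit 1 list in section 7.3.1 includes "Standard questionnaires including the KOOS, IKDC, VR-12 and a Likert pain scale". The order is then clear: "Following randomizing, subjects will undergo a knee aspiration and will receive their first dose study medication". The Visit 1 KOOS is therefore a true pre-treatment score. KOOS is collected again at Visit 2 (before surgery) and at 6, 12 and 24 months.

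The only place that says from where change is measured is the power paragraph of section 10.1.1, which refers to the "standard deviation of the change scores between the day of surgery and one year postoperative visits".

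**The concern.** Three gaps meet in the primary analysis.

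1. The first-choice test does not compare the arms. Friedman's test ranks the repeated scores within each subject and asks whether the visits differ. It has no term for two independent groups.
2. The fallback does compare arms, but its group-by-time contrast between two visits is the difference in mean change. That fixes the slope on the reference score at 1 instead of estimating it.
3. The one stated reference visit comes after the injection. Section 10.1.1 itself predicts a benefit in early pain and function. A score that may already carry the treatment effect is not a baseline.

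At stake are precision and the handling of chance imbalance in a trial of 32 to 40 patients enrolled 1 to 28 days after injury. So is a free choice, after the data are seen, of reference visit and model.

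**Working it through.** **Inputs from the documents (section 10.1.1).** One-year KOOS Quality of Life SD 24.2; target difference 7.2; SD of change 0.2 × 24.2 = 4.8; 16 per group (32 in total), up to 20 per group; alpha 0.05; single time point at one year. The correlation r between reference and one-year score is not given, so I vary it. The SD is for Quality of Life. Using it for Symptoms is an assumption, and it affects the points and power below but not the variance ratios.

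**The plan's own figure.** Effect size 7.2/4.8 = 1.5. Two-sided t-test, 16 per group: power 98.4%. Nine per group would reach 80%. The stated power of at least 80% is therefore true as a lower bound.

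**Correlation implied by the plan's change SD.** With equal SDs, SD of change = SD × √(2(1 − r)). Setting this to 0.2 × SD gives r = 1 − 0.2²/2 = 0.98, for day of surgery to one year.

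**Change from the day of surgery.** If the treatment effect is e at Visit 2 and δ at one year, the change contrast estimates δ − e. A benefit present at surgery and fully kept at one year gives δ − e = 0. The Visit 1 score does not enter at all.

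**Change from Visit 1 against ANCOVA on Visit 1, equal SDs.**
- Change variance is 2(1 − r)SD². ANCOVA residual variance is (1 − r²)SD². The ratio is (1 + r)/2.
- Estimating the slope multiplies the ANCOVA variance by (N − 3)/(N − 4), which is 29/28 at N = 32.
- One standard error of chance baseline imbalance at 16 per group is 24.2 × √(2/16) = 8.6 points. Change scores carry (1 − r) times the imbalance into the estimate, in favour of the arm that starts lower.
- Power is for 7.2 points with score SD 24.2 and 16 per group.

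| Assumed r | (1 + r)/2 | × 29/28 | Shift per 1 SE imbalance (points) | Power, change | Power, ANCOVA |
|---|---|---|---|---|---|
| 0.3 | 0.65 | 0.67 | 6.0 | 10.6% | 13.4% |
| 0.5 | 0.75 | 0.78 | 4.3 | 12.9% | 15.2% |
| 0.7 | 0.85 | 0.88 | 2.6 | 18.3% | 20.1% |
| 0.9 | 0.95 | 0.98 | 0.9 | 44.5% | 45.0% |
| 0.98 | 0.99 | 1.025 | 0.2 | 98.3% | 98.0% |

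Simulation (20,000 trials, 16 per group) gives ratios of 0.68, 0.77 and 1.025 at r = 0.3, 0.5 and 0.98.

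**Break-even.** (1 + r)/2 × 29/28 = 1 gives r = 2 × 28/29 − 1 = 0.93. At N = 40, r = 2 × 36/37 − 1 = 0.95.

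**Interval width.** Taking square roots of the unrounded ratios, the standard error falls by about 18%, 12% and 6% at r = 0.3, 0.5 and 0.7.

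**The case against.** The strongest reply is that r is not in the documents, and that the plan's own change SD implies r = 0.98, where adjustment costs about 2.5% in variance and gains nothing. That stands as arithmetic. But 4.8 rests on a bare 20% assumption. The one reproducibility figure in the protocol, a test-retest ICC above 0.75 in section 7.1.1, does not establish 0.98 across reconstruction and a year of recovery.

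A second reply is that randomisation makes a change-from-Visit 1 comparison unbiased on average. This is correct. The shifts in the table are conditional on the imbalance that happens to occur.

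A reader might infer more than the documents support:

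- *That the primary analysis is a change-from-Visit 1 test that over-corrects imbalance.* The first-choice test is not a change-score test, and the only stated reference visit is the day of surgery. The (1 − r) formula applies to Visit 1 imbalance only if change is taken from Visit 1.
- *That ANCOVA would lift power from 80% to about 89%.* This holds at r = 0.5 only for a standardised effect of 1.02, that is a change SD of about 7.2/1.02 = 7.0, which the plan does not state. Nor can it be combined with the 4.3-point shift, which needs SD 24.2. At r = 0.5 a change SD of 7.0 means a score SD of 7.0. One standard error of imbalance is then 7.0 × √(2/16) = 2.5 points and the shift about 1.2.
- *That baseline adjustment is the only precision gain available.* KOOS at several visits and other Visit 1 variables are also collected.

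**Conclusion.** The point holds in a limited form. The plan collects a pre-injection KOOS-Symptoms score but names no model that compares the arms while adjusting for it, and its only stated reference visit follows treatment. The faults in the Friedman choice and in the day-of-surgery reference do not depend on any assumed correlation.

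The precision gain does. With equal variances and change taken from Visit 1, variance falls by about 33%, 22% and 12% at r = 0.3, 0.5 and 0.7 with 32 patients. It falls by nothing once r reaches about 0.93. The trade is lopsided in favour of adjustment, since the possible loss is about 2.5% at r = 0.98.

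This is not a remedy for power. If the SD is near 24.2 and r is 0.5, power for 7.2 points is about 13% unadjusted and 15% adjusted. By the normal approximation, 80% would need about 178 per arm with change scores and 134 with ANCOVA. The value of the change is a valid, prespecified comparison with a narrower interval.

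**What to change.** In section 10.1.1, make the primary analysis a linear model (ANCOVA) of KOOS-Symptoms at the one-year visit on treatment arm, with the Visit 1 pre-injection KOOS-Symptoms score as covariate. Report the adjusted mean difference with its 95% confidence interval. If normality fails, use rank ANCOVA or a permutation test of the same model in place of Friedman's test. If several visits are modelled, keep the Visit 1 score as a covariate, not an outcome level, treat Visit 2 as post-treatment, and take the one-year contrast as primary.

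Use the same model for KOOS QOL, Pain and Sports/Rec, each with its own Visit 1 score. Align the endpoint wording in the Protocol Summary and section 4.2.1, and put the model in section 10.1.2, where a reader will look for it.

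The cost is a few sentences and one degree of freedom, with no new data, visits or patients. Precision is lost only if r exceeds about 0.93, and then trivially.

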Using the non-parametric Wilcoxon signed-rank sum test, significant differences (p<0.05) were observed in the anakinra treated group only: Pain was reduced in the anakinra treated group of patients by 23% after 4 days, improvement in Activities of Daily Living by 46%, and improvement in total KOOS by 24%; in contrast the placebo group improved by only 4%, 6% and 7% for these outcomes, respectively. This suggests a significant early effect in this patient population that is beneficial for the early rehab process prior to surgery(22).

Synovial fluid IL-1 α decreased over 1 month in response to a single IL-1Ra intra-articular injection in our pilot trial. The change with treatment (Day 0 to Day 28) in synovial fluid IL-1 α constituted the most intriguing and promising cytokine result from this pilot trial. IL-1 α increased in all the placebo treated patients (n=4 pairs of samples available); whereas IL-1 α decreased in 4 or 5 of the anakinra treated patients (n=5 pairs of samples available)(21).

Study 3: In order to prove that we have the ability to perform a high level (GCP) randomized clinical trial our group has performed a randomized clinical trial involving ACL patients in the same study design featuring identical enrollment (inclusion/exclusion) criteria as the one proposed in this contract (MOON-AAA Clinicaltrials.gov identifier: NCT01692756). In this multicenter early intervention trial testing the effect of Triamcinolone administration patients underwent knee joint aspirations, blood draws and urine collections at three time points prior to ACL surgery.

Table 1: Enrollment data MOON-AAA trial						
	range mean					
AGE	13-33	18.58				
M:F	Male: 25	Female: 18				
BMI	19.1-31.6	24.25				
t visit 1	1-8	4.17				
t visit 2	7-20	11.53				
t surgery	10-51	28.94				

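### In the non-parametric branch of section 10.1.1, the test named for comparing KOOS between groups (Friedman) ignores treatment arm and so cannot test the drug effect

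*Combined protocol and SAP*

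**What the plan says.** The design is two parallel arms, up to 20 patients each, with every patient in one arm only (section 4.1). The primary endpoint is KOOS-Symptoms (4.2.1). Section 10.1.1 states the primary aim as greater improvement on the drug one year after surgery. KOOS is collected at Visits 1, 2, 4, 5 and 6 (7.3.1, 7.3.2), and the injection is given at Visit 1.

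Section 10.1.1 sets out two analysis routes. The first is introduced because data from a sample of this size may not be normal. In it, KOOS "will be analyzed for change between groups using Friedman two-way ANOVA for repeated measures". The second applies if data are normal or can be transformed to be so: "then repeated measures ANOVA will be utilized comparing treatment groups".

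The power calculation in the same section uses a different model, "One-way ANOVA model with alpha = 0.05, Effect size = 7.2/4.8 = 1.5", and says that the outcome was "instead analyzed at a single time point (oneyear follow-up". It also remarks that the relative efficiency "of the Wilcoxon test is at least 0.95), leading us to conclude that our parametrically based power calculations should apply" to a non-parametric analysis.

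Section 10.1.2 carries the heading for the primary efficacy analysis but opens with "A safety review of treatment Groups 1 and 2will be performed" and then lists stopping criteria. Section 10.1.3, for secondary endpoints, is marked not applicable.

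**The concern.** The sentence gives Friedman's test a job that it cannot do. The two ways in its name are block (patient) and repeated condition (visit), not arm and visit. It could compare treatments only if each patient received both, and here none does.

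Knee scores can be expected to rise after injury and reconstruction in both arms. A test of whether visits differ will then tend to be significant whether or not the drug works. Conversely, arms that move apart around a flat average can leave it non-significant. If the non-parametric route is taken as written, the primary p-value says nothing about the drug, and a between-arm test would have to be supplied from outside the plan.

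**Working it through.** **1. The plan's own power figure.** Inputs from 10.1.1: difference 7.2, change-score SD 0.2 × 24.2 = 4.84 (given as 4.8), 16 per arm, alpha 0.05. Effect size 7.2/4.8 = 1.5. Noncentrality 1.5 × √(16/2) = 4.24. Normal approximation: Φ(4.24 − 1.96) = 98.9%. The exact t-test, which equals the two-group one-way ANOVA, gives 98.4%. The claim of at least 80% is true as a lower bound. That calculation is between arms at one time point; Friedman is neither.

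**2. Arm is absent from the statistic.** With n patients, k visits and R_j the sum over patients of the within-patient ranks at visit j:

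Q = 12 / [n k (k+1)] × Σ R_j² − 3 n (k+1)

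With n = 32 and k = 5, Q = 0.0125 × Σ R_j² − 576. Each R_j is a sum over all patients, so relabelling arms changes nothing. In one simulated trial with a 15-point drug effect, 1,000 reshuffles of the arm labels all gave 41.825. This is algebra and needs no assumption about the data.

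**3. Rejection with no drug effect.** The setting was 16 per arm, normal scores at the five KOOS visits, SD 20 and within-patient correlation 0.5. Shared recovery followed the shape 0, 1/3, 0.73, 0.93, 1 of its total. There were 20,000 trials per scenario at two-sided 0.05. The SD, correlation, recovery size and shape are assumptions; the documents give none for KOOS-Symptoms.

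| Shared recovery (points) | Friedman, arms pooled | Rank-sum between arms, Visit 5 minus Visit 2 |
|---|---|---|
| 0 | 5% | 4–5% |
| 5 | 18% | 4–5% |
| 15 | 96% | 4–5% |
| 30 | 100% | 4–5% |

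Sensitivity of the Friedman column:
- SD 15 to 25, or correlation 0.3 to 0.7: 13–31% at 5 points and 82–99.9% at 15.
- Three other recovery shapes: 16–29% at 5 points and 93–99.9% at 15.
- Visits 2, 4, 5 and 6 only: 9% at 5 points, 59% at 15 and 99.7% at 30.
- Scores scaled to the plan's change SD of 4.84: 46% at 2 points and 100% at 5.

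**4. Arms run separately.** With n = 16 in each arm, Friedman rejects in about 10.5% of arms at 5 points and 68% at 15. Neither result compares arms. At 15 points with no drug effect, the chance that exactly one arm is significant is 2 × 0.68 × 0.32 = 44%.

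**5. The opposite failure.** Suppose the arms diverge by 7.2 points (+3.6 and −3.6) around a flat mean, with change SD 4.8 and 16 per arm. Friedman rejects in 1.5% of trials and rank-sum on change in 97.8%.

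**6. Power of a between-arm rank test.** Under the plan's inputs (7.2 points, SD 4.84), rank-sum power is 97.6% at 16 per arm and 99.4% at 20. Step 3 implies a different change SD: 20 × √[2 × (1 − 0.5)] = 20. The effect size is then 7.2/20 = 0.36, and rank-sum power is about 16% at 16 per arm and 19% at 20. The two sets of inputs are not compatible, and the documents do not settle which is nearer the truth for KOOS-Symptoms.

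**7. Baseline.** The change score in 10.1.1 runs from the day of surgery (Visit 2), after the injection. If the benefit is D2 at Visit 2 and D5 at Visit 5, that change score sees D5 − D2. A 7.2-point benefit present by Visit 2 and maintained gives 7.2 − 7.2 = 0, and is detected about 5% of the time. Measured from Visit 1 it gives 7.2 − 0 = 7.2, detected about 98% of the time if the plan's SD also held for that change.

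**The case against.** The route is conditional: non-parametric methods may be used, and the parametric alternative does compare treatment groups. That stands, and it limits the defect to one branch. A reader might infer that the trial has no valid primary analysis at all. The documents do not support this, because repeated measures ANOVA with arm as a factor can answer the question, although no contrast or visit is named.

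A reader might also infer that the between-arm test must now be chosen with the results in view. That goes too far. A test can still be named before unblinding, and 10.1.1 promises blinded data analysis. The remark on Wilcoxon efficiency suggests that the authors had a two-sample rank test in mind. But it concerns power and assigns no test to KOOS.

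The rejection rates in step 3 assume one Friedman test on pooled arms, which the text does not specify. Separate tests give lower rates (step 4). That changes the size, not the defect.

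Finally, it is tempting to call the synovial-fluid test a second error: "Synovial fluid analyses comparing the three groups at five time points will be analyzed using the Wilcoxon Signed Rank Sum Test". The name suggests a paired test, and the pilot used a similar one for a within-arm result (2.1: "Using the non-parametric Wilcoxon signed-rank sum test, significant differences (p<0.05) were observed in the anakinra treated group only"). Here, though, the sentence speaks of comparing groups, and the power remark treats Wilcoxon as the analog of the two-group comparison, so a two-sample test is the more natural reading. The wording needs clarifying; it does not establish a wrong test.

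**Conclusion.** The Friedman sentence is wrong as written and should be corrected before unblinding. That arm plays no part in the test follows from its definition and rests on no assumption. The size depends on unstated inputs. With no drug effect, a pooled test rejects in about 18% of trials at 5 points of shared recovery and 96% at 15, under SD 20, correlation 0.5 and 16 per arm. A between-arm rank-sum test holds about 5%. The defect is confined to the non-parametric branch, and no other section fills the gap.

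The rank-sum power of about 97% shows only that changing the test costs little under the plan's own inputs. Those are KOOS Quality of Life figures applied to the day-of-surgery change. A reader might take the figure as support for 16 per arm on KOOS-Symptoms. It is not, since power would be about 16% at a change SD of 20.

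**What to change.** In 10.1.1, replace Friedman with one pre-specified between-arm test of KOOS-Symptoms at the one-year visit (Visit 5), and state it in 10.1.2. Suitable choices are a rank-based ANCOVA adjusted for the pre-injection Visit 1 score, or a Wilcoxon rank-sum test on change from Visit 1. If repeated measures ANOVA is kept for normal data, name the arm-by-visit contrast at Visit 5. If the day-of-surgery baseline is kept, say that any benefit already present by Visit 2 cancels from the change score.

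The cost is wording only: no new patients, visits or data. It does require a decision on baseline. Moving to Visit 1 means justifying the change SD afresh, because 4.8 was set for the change from surgery.

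Separately, correct the synovial-fluid sentence. Its three groups and five time points conflict with two arms (4.1) and with aspiration at no more than Visits 1, 2 and 3 (7.1.1, 7.3.2). State the visits actually aspirated. Visit 2 aspiration is omitted in unoperated patients. Whether Visit 3 covers everyone differs between 7.1.1, 7.3.1 and note h of 7.3.2, and those must be reconciled.

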4 STUDY DESIGN AND ENDPOINTS

4.1 DESCRIPTION OF THE STUDY DESIGN

This is a phase 2, prospective, randomized, triple-blinded, placebo-controlled study of IL-1RA treatment in patients with acute ACL tear and painful effusions. The study population will include up to 40 participants within 28 days of injury. The study is open to male and female participants who are between the ages of 14 and 40, who have ACL tears. Once enrolled will be randomized into 2 groups (20 subjects per group).

- **Group 1** will receive intra-articular injection of Anakinra (Kineret®, IL-1ra; 150mg) 1-28 days after ACL injury.
- **Group 2** will receive intra-articular injection of saline placebo 1-28 days after ACL injury.

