4.2.2 SECONDARY ENDPOINTS

KOOS QOL, KOOS-pain, KOOS-Sports/Rec, Biomarker levels in synovial fluid, serum and urine at time of surgery MRI T1rho changes at 2 years

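### The non-parametric route for comparing synovial biomarkers between arms names a paired, within-patient test (Wilcoxon signed-rank), which cannot compare two independent arms

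*Combined protocol and SAP*

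**What the plan says.** Section 10.1.1 (Statistical analyses) allows for non-normal data in a study of this size: "Therefore, non-parametric statistical measures may be used". For synovial fluid it then states: "Synovial fluid analyses comparing the three groups at five time points will be analyzed using the Wilcoxon Signed Rank Sum Test with Hochberg corrections", the correction being across time points. The next sentence gives the alternative. If the data are normal, or can be made so by a transformation such as the log, "then repeated measures ANOVA will be utilized comparing treatment groups".

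The design is parallel-group. Section 4.1 has patients "randomized into 2 groups (20 subjects per group", and no matching of patients across arms is described. Section 4.2.2 lists as a secondary endpoint "Biomarker levels in synovial fluid, serum and urine at time of surgery". Section 10.1.1 frames the biomarker aim and its power statement (effect size 1.34, 16 per group, at least 80%) as a comparison between groups. Section 10.1.3, which should describe the analysis of secondary endpoints, says only that it does not apply.

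The same test name appears once more, in the account of the randomized pilot in section 2.1: "Using the non-parametric Wilcoxon signed-rank sum test, significant differences (p<0.05) were observed in the anakinra treated group only". There it goes with changes inside the anakinra arm in pain, daily living and total KOOS. The placebo changes are only described alongside.

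**The concern.** A signed-rank test asks whether patients in one sample changed. The biomarker aim asks whether drug patients changed differently from placebo patients. If the sentence is followed literally, the test can be run only within each arm, and the drug-versus-placebo question is left to an informal comparison of two p-values.

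That comparison is unsafe here because the protocol expects markers to move after injury without treatment. Section 2.1 describes IL-1ra falling and IL-1β rising after ACL rupture. Section 7.2.1 describes CTX-II and xanthine oxidase rising in the first month. If both arms move, chance decides which arm crosses 0.05. The synovial part of the first secondary objective could then yield an unfounded mechanistic claim, or miss a real effect.

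**Working it through.** **1. The plan's own figure.** Inputs from section 10.1.1: effect size d = 1.34, n = 16 per group, alpha 0.05 (taken as two-sided, since sidedness is not stated). For two independent groups, power ≈ Φ(d·√(n/2) − 1.96) = Φ(1.34 × √8 − 1.96) = Φ(3.79 − 1.96) = Φ(1.83) = 96.6%. The two-sample t version gives 95.6%. The stated at least 80% is therefore true, and these are two-sample calculations. The planned comparison is between arms, so the named test does not match its own power basis.

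**2. What each test examines.** Let D be a patient's change in log concentration from Visit 1.
- Signed-rank, within one arm: the null is that D is symmetric about 0 in that arm.
- Rank-sum, between arms: the null is that D has the same distribution in both arms.

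If both arms change by the same amount δ ≠ 0, the first null is false and the second is true. The first test then says nothing about the drug.

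**3. Size of the error if one-arm significance is read as a drug effect.** Let p be the chance that one arm is significant. With no drug effect and independent arms, P(drug arm only) = p(1 − p). This cannot exceed 25%, and P(exactly one arm) cannot exceed 50%. Changing the significance level, as Hochberg does, moves the δ at which the peak occurs but does not remove the peak.

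Simulation: 3,000 trials per row, 16 per arm, normal changes with SD 1, no drug effect. The common change δ is an assumption, because the documents give none.

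| δ (SD) | drug arm significant | placebo arm significant | product for drug only | drug only, simulated | exactly one arm | rank-sum rejects |
|---|---|---|---|---|---|---|
| 0 | 0.041 | 0.039 | 0.041 × 0.961 = 0.039 | 0.039 | 0.076 | 0.045 |
| 0.25 | 0.138 | 0.139 | 0.138 × 0.861 = 0.119 | 0.118 | 0.238 | 0.051 |
| 0.50 | 0.418 | 0.428 | 0.418 × 0.572 = 0.239 | 0.235 | 0.481 | 0.047 |
| 0.75 | 0.760 | 0.760 | 0.760 × 0.240 = 0.182 | 0.184 | 0.369 | 0.041 |
| 1.00 | 0.946 | 0.958 | 0.946 × 0.042 = 0.040 | 0.040 | 0.093 | 0.048 |

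The simulation error at the peak is √(0.235 × 0.765 / 3000) = 0.008. With 20 per arm the drug-only column becomes 0.051, 0.151, 0.237, 0.110 and 0.019, so enrolling the full 40 does not cure it. For a marker that rises naturally, the pattern that looks like benefit is placebo-only significance, which is equally frequent by symmetry.

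**4. When the drug works.** With a true difference of 1.34 SD and 16 per arm, the drug-only pattern depends on where the placebo arm sits. It appears in 95% of trials if placebo does not change, 33% if the arms change by 0.67 and 2.01 SD, and 22% if they change by −0.67 and +0.67 SD. The rank-sum test has about 94% power in all three cases (98% with 20 per arm), before Hochberg. The effect size is borrowed: the plan states it for biomarkers at one year, when no synovial fluid is taken.

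**5. The rest of the sentence.** Section 4.1 has two arms, not three. Section 7.1.1, section 7.3.1 and the schedule in section 7.3.2 allow at most three aspirations: Visit 1 (before injection), Visit 2 for those who have surgery, and Visit 3 for those who had surgery and have fluid. Visits 5 and 6 collect only serum and urine. Five synovial time points do not exist.

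**The case against.** The strongest reply is that the plan already has a valid between-arm analysis. The non-parametric route is conditional, and the very next sentence gives repeated measures ANOVA between treatment groups, including on the log scale, where such concentrations are often analysed. This stands. A reader might infer that the trial has no valid drug-versus-placebo comparison of biomarkers; the documents do not support that.

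A second reply is that the printed name blends signed-rank with rank-sum, and the sentence states a between-group purpose, so this may be a slip of the pen. That is possible. But section 2.1 uses the same blended name for within-arm results, and section 10.1.3 supplies nothing to settle it. If it is a slip, the correction is still needed.

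A third reply is that nothing in the plan says a drug effect will be declared from significance in one arm. This also stands. A reader might infer that about a quarter of null trials will yield a false drug claim, but that figure is the peak of an assumed range and depends on a way of reading results that is seen only in the pilot account. Sections 2.1 and 7.2.1 make a common change plausible but give no size for it between Visit 1 and surgery.

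Finally, the scope is narrow. The sentence covers synovial fluid, not serum or urine. The one-year biomarker comparison behind the power statement cannot use synovial fluid. KOOS has its own named test.

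**Conclusion.** The concern holds, within limits. As written, the non-parametric test named for comparing synovial biomarkers between arms is a paired test and cannot compare independent arms. The defect is confined to that route and that fluid; the ANOVA route and the primary endpoint are not affected by it.

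The numerical risk is conditional. If the test is run arm by arm, one-arm significance is read as a drug effect, there is no drug effect, and 16 patients per arm have normal change scores, then drug-arm-only significance occurs in about 4% to 25% of trials as the common change runs from 0 to 1.0 SD, with the peak near 0.5 SD. The rank-sum test stays near 5% throughout. The stated power for effect size 1.34 survives the correction, so the sample size is not at issue.

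**What to change.** In section 10.1.1, replace the named test with the Wilcoxon rank-sum (Mann-Whitney) test between the two arms, applied to log change from the pre-dose Visit 1 sample. Apply it at the synovial visits that exist: Visit 2, and Visit 3 where an aspirate was taken. Keep Hochberg across those time points, and keep the repeated measures ANOVA for normal or transformable data. An ANCOVA of log concentration adjusted for the log Visit 1 value is a reasonable option but is not required.

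In the same sentence, change three groups to two, and replace five time points with the at most three aspirations in the schedule. Sections 7.3.1 and 10.2.1 carry the same count of three groups and should be aligned. State which participants contribute at each visit, since those without surgery have no Visit 2 aspirate and Visit 3 depends on surgery and on fluid being present. Add that within-arm tests are descriptive and support no treatment claim.

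The cost is SAP wording, to be settled before unblinding. No new data, visits or patients are needed.
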